In this study, we will perform a post-approval mechanistic study. We will perform a mechanistic study using FDA-approved devices that will be used in accordance with approved labeling. We will implement a randomized, double-blind, placebo-controlled, crossover study. This study design will allow us to test the physiological effects of multiple forms of SCS within individual participants. It will also allow us to quantify the effects of sham stimulation. We believe variability in SCS are largely due to “placebo” effects and/or lack of understanding of their mechanisms of action. A majority of previous clinical studies were performed in an unblinded manner whose results may have been confounded by a “placebo” effect.^{1,7–9,57} One major criticism of previous SCS studies is the absence of blinding due to the presence of stimulation-induced paresthesia(s). With the advent of paresthesia-free SCS waveforms, such as Burst-SCS and KHFSCS, the paradigm is shifting. Clinical studies using Burst-SCS and KHFSCS have reported success in stimulating without producing paresthesias. However, a majority of these studies were performed in an unblinded manner. Therefore, the effect of “placebo” remains to be quantified. Comparing the physiological effects of Burst-SCS and KHFSCS to sham (no) stimulation will help systematically control for placebo effects and will help identify the true pain-relieving effects of SCS. For the fourth and final treatment allocation, all participants will receive seven days of tonic 50 Hz SCS that will generate paresthesias over their painful areas. This treatment is performed last because participants will likely know that they are receiving active stimulation due to the paresthesias and this design will minimize the chance of breaking the blind during the previous treatments. During the study, subjects will be instructed to maintain a stable level of medications for control of chronic pain symptoms.

As described in Section 9.5, the primary outcome will be SCS-induced changes in temporal summation (TS). TS refers to an increased perception of pain in response to sequential stimuli of equal physical strength (Fig. 9.1A). It is a quantitative sensory testing (QST) model of neural plasticity and central hyper-excitability that is thought to reflect the

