 - Discomfort threshold
 - Paresthesia mapping
- Documentation of any adverse events
- Computed tomography (CT) scan

*At the end of the Visit 2, randomization will occur. We will randomize participants to one of six randomly allocated sequences that each contain four treatments: burst, 1 kHz, sham, and 50 Hz SCS. Participants will receive each treatment for seven days.

Treatment (Visit 3)

After participants have received approximately seven days of the first treatment, we will perform the study procedures listed below. After performing these study procedures, the stimulation parameters will be adjusted to apply the second treatment allocation in the respective treatment arm. Participants will be blinded during programming.

- Collect vital signs (heart rate, blood pressure, respiration rate, body temperature, height and weight)
- Review and record any changes in concomitant medications
- Rate participants current pain on a scale Visual Analog Scale (VAS) and SFMPQ
- Collect
 - Pain disability Index (PDI)
 - Short Form McGill Pain Questionnaire (SFMPQ)
 - Michigan Body Map (MBM)
 - PainDETECT
 - Brief Pain Inventory [BPI]
 - Visual Analog Scale (VAS) and SFMPQ
 - Coping Strategies Questionnaire (CSQ)
 - Hospital Anxiety and Depression Scale (HADS)
 - EQ-5D Health Questionnaire
 - Fibromyalgia Survey Questionnaire (FSQ)
- Conditioned Pain Modulation (CPM) Test – Assessment to examine how the body naturally controls pain
- Measure participant's sensitivity to different stimuli
 - Vibrometer Test
 - Algometer Test
 - PinPrick Test (Temporal summation)
 - Multimodal Automated Sensory Test (MAST)
- Deliver treatment (Burst, 1kHz, or Sham SCS)

- Stimulator programming
 - Perception threshold
 - Discomfort threshold
 - Paresthesia mapping
- Documentation of any adverse events

Treatment (Visit 4)

After participants have received approximately seven days of the second treatment, we will perform the study procedures listed below. After performing these study procedures, the stimulation parameters will be adjusted to apply the third treatment allocation in the respective treatment arm. Participants will be blinded during programming.

- Collect vital signs (heart rate, blood pressure, respiration rate, body temperature, height and weight)
- Review and record any changes in concomitant medications
- Rate participants current pain on a scale Visual Analog Scale (VAS) and SFMPQ
- Collect
 - Pain disability Index (PDI)

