9.2 Sample Size and Randomization

The primary endpoint will be spinal cord stimulation (SCS)-induced changes in temporal summation (TS). We will calculate TS scores by subtracting the average pain rating of the single-stimulus trials from the average pain rating of the ten-stimuli trials (see Section 9.5.1). If the difference is a positive number, we will conclude that there was pain summation, where larger numbers will indicate increased pain summation or TS. If the difference is zero or a negative number, we will conclude that there was no pain summation or TS. As described in Section 3, we will consider four types or factor levels of SCS: Burst-SCS, KHFSCS, 50 Hz SCS, and Sham SCS. We will consider a repeated-measures design in which all four levels are tested in each participant. We will employ linear mixed-effects models in our analysis. Therefore, our null hypothesis will be that the group means with regards to TS are all equal. Our alternate hypothesis will be that the not all of the group means of TS are equal. If we can reject the null

hypothesis, we will perform the appropriate post-hoc analyses to determine specific differences. To determine specific treatment effects, we will perform the following pairwise tests: Burst vs. Sham, 1 kHz vs. Sham, and 50 Hz vs. Sham. These tests do not require an adjustment for multiplicity because they are hierarchical.

We will perform statistical analysis on SCS-induced changes in TS measured by differences in the corresponding TS. For our study, we assumed a sample size of 20 (25 recruited with an attrition rate of 20% that was estimated from prior SCS studies that employed a similar crossover study design^{39,41}), 80% power, and 5% level of significance with two-tailed tests. Using a paired t test, this will allow us to detect a within-subject effect size (i.e., standardized difference score, d_z) of 0.68, reflecting the difference between active and sham SCS. While this study is exploratory, in the most comparable study conducted to date, eight subjects with neuropathic pain underwent SCS.⁶¹ Assuming a correlation value of 0.5 between TS measured in the same subject, the d_z for the effects of “ON” versus “OFF” stimulation was 0.89. A similar effect size in our study will achieve a statistical power greater than 95% with a sample size of 20.

Treatment Assignment Procedures

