We will have two research teams. One team will be unblinded and will perform stimulator programming/adjustment, and the other team will be blinded and will perform clinical testing and collect study outcome measures.

Within two months of enrollment, we will randomize subjects to one of six randomly-allocated sequences consisting of the following treatments: burst, 1 kHz, sham, and 50Hz SCS. Subjects will receive each treatment for seven days following one of the six randomly allocated sequences (crossover design) (Fig. 3.1). We will perform testing before randomization and at the end of each seven-day treatment period.

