Participants will be blinded during programming. During the stimulator programming session, we will adjust the settings on the subjects' SCS device. We will adjust the settings such that subjects will receive seven days of a specific treatment allocation. To ensure proper blinding during the first three treatment allocations, we will set the stimulation amplitude so that the participants do not feel any stimulation-induced paresthesias. Sham SCS will be performed by setting the amplitude to 0 mA. For some systems, if the stimulation amplitude is decreased to 0 mA, the system will report that the stimulation is OFF and the participants will know that they are not receiving stimulation. For these systems, we will perform sham SCS by setting the stimulation parameters to their minimal values: pulse width (~20 μ s), frequency (~2 Hz), and amplitude (~0.1 mA). Therefore, participants will not experience stimulation-induced paresthesias during Sham SCS. However, during an active treatment allocation, stimulation-induced paresthesias may sometimes occur (usually as a tingling sensation) due to positional changes (e.g., bending, lifting) and/or extreme movement. To minimize the occurrence of these stimulation-induced paresthesias, we will have the participants assume multiple positions (e.g., sitting, standing, supine, prone) during the programming session and ensure that the stimulation amplitude is low enough to avoid stimulation-induced paresthesias in any of these bodily positions. Therefore, the participant experience should be similar for the first three treatments. After completion of the first three treatment allocations, each participant will receive seven days of tonic 50 Hz SCS that will generate paresthesias over their painful areas. While having 50 Hz SCS as the last treatment in all participants may introduce a potential order effect, this treatment will be performed last because patients will likely know that they are receiving active stimulation due to the paresthesias and this design will minimize the chance of breaking the blind during the first three treatment allocations.

Participants will be instructed not to adjust the stimulation settings during each treatment. At the end of each treatment allocation, we will interrogate the participant's implanted stimulator to ensure that the stimulation settings were not altered during the specific treatment

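### 50 Hz SCS is always the fourth period and likely recognised by participants, so including it in the primary four-mean test and testing it against Sham mixes treatment with time and expectation

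*Combined protocol and SAP*

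**What the plan says.** Section 3 fixes the position of 50 Hz: "For the fourth and final treatment allocation, all participants will receive seven days of tonic 50 Hz SCS". Section 6.2 describes the randomisation: "We will randomize participants to one of six randomly allocated sequences that each contain four treatments: burst, 1 kHz, sham, and 50 Hz SCS". With 50 Hz always last, the six sequences are the six orders of the other three treatments.

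The reason given for the fixed position is to protect the blind in periods 1-3, because with 50 Hz "participants will likely know that they are receiving active stimulation due to the paresthesias". Section 9.2 concedes the cost: "While having 50 Hz SCS as the last treatment in all participants may introduce a potential order effect". It also sets up two study teams. One programs the stimulator unblinded; "the other team will be blinded and will perform clinical testing and collect study outcome measures".

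For the analysis, section 9.2 says "our null hypothesis will be that the group means with regards to TS are all equal", with 50 Hz as one of the four levels. If that null is rejected, "we will perform the following pairwise tests: Burst vs. Sham, 1 kHz vs. Sham, and 50 Hz vs. Sham". These tests are not adjusted for multiplicity, on the ground that they are hierarchical. Sections 9.1 and 9.6 specify a linear mixed model with a participant random intercept and two-sided p < 0.05. They name no period term, and neither section gives 50 Hz a separate status.

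**The concern.** In a crossover trial, treatments are compared fairly because each one appears equally often in each period. That holds here for Burst, 1 kHz and Sham, but not for 50 Hz. Whatever changes TS between the first three periods and the fourth is counted as an effect of 50 Hz.

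Two such influences are plausible. Under the schedule in section 6.1, the 50 Hz reading at Visit 6 is the fifth full pin-prick session (Visits 2 to 6), after a familiarisation session at Visit 1. In addition, TS is built from the participant's own 0-100 ratings (section 9.5.1), in the one period when the participant probably knows that stimulation is on.

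Two results are at stake: the 50 Hz vs Sham comparison, and the primary omnibus test, which a period-4 shift alone can reject. The bias can create an apparent effect or hide a real one.

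**Working it through.** **1. The plan's own figure.** Inputs from section 9.2: 25 recruited, 20% attrition, two-sided 5%, paired t test. 25 × 0.8 = 20. With the exact noncentral t (noncentrality d_z × √n), d_z = 0.68 at n = 20 gives 0.68 × √20 = 3.04 and power 82.2%; n = 19 already gives 80.0%. d_z = 0.89 gives 96.5%. The stated figures reproduce and are slightly conservative. The sample size is not the problem; 0.68 serves below as a yardstick.

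**2. Can treatment and period be separated?** Rank of the fixed-effect design matrix over the six sequences:
- Four periods, categorical period: 1 + 3 + 3 = 7 columns, rank 6. 50 Hz and period 4 are the same column.
- Four periods, linear period: 1 + 3 + 1 = 5 columns, rank 5. This is estimable, but the 50 Hz column absorbs period 4, so the slope comes from periods 1-3 alone and is extrapolated.
- Periods 1-3 only, categorical period: 1 + 2 + 2 = 5 columns, rank 5. Fully estimable.

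**3. Size of the bias.** Let π_k be the non-treatment level of TS in period k. With balanced sequences and no treatment effect,

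E(50 Hz − Sham) = π₄ − (π₁ + π₂ + π₃)/3.

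For linear drift d per period this is 4d − (1 + 2 + 3)d/3 = 2d. For Burst − Sham and 1 kHz − Sham it is 0. With d in residual SDs, the SD of a paired difference is √2, so the spurious d_z is 2d/√2 = 1.41d. A spurious 0.68, the effect the trial is sized for, needs d = 0.68/1.41 = 0.48 residual SD per period.

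**4. Error rates under the planned model.** Simulation with n = 20, complete data, near-balanced sequences, no treatment effect and no period term; omnibus F(3, 57) and pooled-error contrasts. The values of d are assumptions. Repeat runs move the rates by one or two percentage points.

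| d (residual SD per period) | Spurious d_z, 50 Hz vs Sham | Omnibus falsely rejects | False 50 Hz claim, after omnibus gate | False 50 Hz claim, no gate |
|---|---|---|---|---|
| 0 | 0 | 5% | 2% | 5% |
| 0.1 | 0.14 | 8% | 4% | 9% |
| 0.2 | 0.28 | 21% | 13% | 22% |
| 0.25 | 0.35 | 29% | 20% | 31% |
| 0.5 | 0.71 | 85% | 76% | 82% |

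The gated column follows section 9.2, where the pairwise tests come only after the omnibus null is rejected.

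**5. The randomised comparisons.** In the same runs, Burst vs Sham and 1 kHz vs Sham each reject about 4-5% of the time. A gated false claim on either one rises only from about 3% without drift to about 7% at d = 0.5.

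**6. A shift in period 4 only.** With shifts of 0.25, 0.5 and 0.68 paired-difference SDs, the omnibus test falsely rejects 17.5%, 58.8% and 86.9% of the time, and gated 50 Hz claims occur 10.9%, 48.1% and 80.2% of the time. A linear period term would not help here, because periods 1-3 show no slope.

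**The case against.** The other side has a good deal that stands.

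- Placing 50 Hz last protects the blind in periods 1-3, and the plan discloses the order effect. The study calls itself an exploratory pilot. None of this changes the arithmetic: the disclosure is not carried into the null hypothesis, the model or the interpretation of the contrast.
- TS is a difference between two ratings from the same session, so drift that shifts both ratings equally cancels. Familiarisation and a full test also precede period 1. Both make large drift less likely, and d = 0.5 is an extreme case. Neither deals with expectation in period 4.
- The omnibus gate lowers the false 50 Hz rate, to below 5% at d = 0.1. If hierarchical means a fixed sequence with 50 Hz last, false 50 Hz claims with no treatment effect at all stay under 0.5%. The text does not settle that reading, and it would not remove the confounding if Burst and 1 kHz truly work.

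A reader might infer that a false omnibus rejection compromises Burst and 1 kHz as well. Step 5 does not support that. A reader might also infer that no model can separate 50 Hz from time, or that any time trend biases the result. Both go too far: a linear term is estimable by extrapolation, and only a trend that sets period 4 apart from the mean of periods 1-3 matters. Nor is the 50 Hz period simply open-label. The testers are blinded, and section 6.2.1 withholds treatment type and order from participants until debriefing. What is expected is that participants will recognise active stimulation.

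**Conclusion.** The concern holds for two results: the primary four-mean test and 50 Hz vs Sham. The aliasing with categorical period follows from the design and needs no assumption. The error rates do rest on assumptions, namely drift size and shape, complete data on 20 participants and a random-intercept model. Across the assumed drifts of 0.1 to 0.5 residual SD per period, the omnibus error runs from about 8% to 85%, and gated false 50 Hz claims from about 4% to 76%. The documents do not show that any drift exists, so these figures measure exposure and do not predict what will happen. The documents do not support extending the criticism to the two randomised, blinded comparisons with Sham.

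**What to change.** In sections 9.2 and 9.6:

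1. Define the primary null hypothesis and its follow-up tests on Burst, 1 kHz and Sham (periods 1-3), with period as a fixed effect beside the participant random intercept.
2. Report 50 Hz vs Sham separately, as an estimate with a confidence interval, labelled non-randomised, likely unblinded to participants and confounded with period. Make no claim of a treatment effect from its significance.

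The treatment order stays as it is. In simulation, the three-treatment omnibus test with a period term rejects 5.1%, 4.9% and 5.1% of the time at linear trends of 0, 0.2 and 0.34 paired-difference SDs per period. Power for one active treatment vs Sham at d_z = 0.68 with n = 20 is about 84%, with or without the trend, so the sample size still suffices for Burst and 1 kHz. The change is wording only. Its cost is the formal 50 Hz vs Sham test, whose p-value has no clean causal reading in this design.

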9.6 Data Analyses

Analysis of the primary efficacy endpoint(s): The primary endpoint will be SCS-induced changes in temporal summation (TS) (see Section 9.5.1). We will use a repeated-measures approach in which the continuous TS values will be calculated at the end of each seven-day treatment period, i.e., type of SCS. To analyze SCS-induced changes in TS measured at the end of each treatment period, we will use linear mixed-effects models that will include a participant-level random intercept to account for correlations of measurements from the same participant. We will obtain the least-squares estimates of the mean TS for the treatments and perform group comparisons with the appropriate contrasts. We will establish statistical significance with two-sided $p < 0.05$. We will utilize a per-protocol analysis dataset. We will only consider randomized participants who completed the Sham SCS treatment along with at least one other active (i.e., burst, tonic 1 kHz, tonic 50 Hz) SCS treatment along with the associated outcome measures for each treatment.

Analysis of the secondary endpoint(s): N/A.

Baseline descriptive statistics: We will use descriptive statistics to assess data quality and characterize relationships between variables. We will list the aggregate data using means and standard deviations for normally distributed data and medians and interquartile ranges for non-normal data. We will consider several baseline demographics and clinical characteristics, such as gender, pain duration, pain diagnosis, previous back surgery, and co-treatments (e.g., opioids, antidepressants, anticonvulsants, NSAIDs/simple analgesics, other). We will consider the QST outcome measures characterizing baseline static and dynamic pain processing. Finally, we will also consider the exploratory outcome measures related to baseline pain intensity, pain quality, pain spread, and quality of life.

Sub-group analyses: This study is an exploratory mechanistic study examining the physiological effects of multiple forms of SCS on sensory processing. Due to the small number of participants that will be considered in this study (i.e., $n=20$), we will not analyze primary or exploratory endpoints based on age, race/ethnicity, or other demographic characteristic(s). However, sex has been shown to be an important variable to consider in chronic pain and sensory processing. Therefore, although we may not detect significant differences due to the

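### Section 9.2 waives multiplicity adjustment for the three Sham contrasts as hierarchical, but writes no order or stop rule; family-wise error reaches about 9% if exactly one waveform works

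*Combined protocol and SAP*

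**What the plan says.** Section 9.2 sets the null hypothesis that the four treatment means on TS are equal. If it is rejected, post-hoc analyses follow, and three are named: Burst, 1 kHz and 50 Hz, each against Sham. The section then says: "These tests do not require an adjustment for multiplicity because they are hierarchical".

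The sample-size text in the same section assumes 20 evaluable participants out of 25, with "80% power, and 5% level of significance with two-tailed tests". It continues: "Using a paired t test, this will allow us to detect a within-subject effect size (i.e., standardized difference score, d_z) of 0.68". For context it cites a small earlier study in which "the d_z for the effects of “ON” versus “OFF” stimulation was 0.89", and says that an effect of that size would give power above 95%.

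Section 9.6 specifies a linear mixed model with a participant random intercept and says the analysis will "perform group comparisons with the appropriate contrasts", at two-sided p below 0.05. It does not repeat the omnibus condition and gives no testing order. Nowhere do the documents say that one Sham contrast is tested only if another is significant.

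**The concern.** A set of tests needs no adjustment on grounds of hierarchy when each test is reached only through a significant result on the one before it. The text describes something else: one gate in front of three parallel tests. An omnibus gate protects against false claims when nothing works. Once one waveform truly differs from Sham the gate is likely to open, and two true null hypotheses are then each tested at 0.05 with nothing between them.

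What is at stake is the set of active-versus-Sham conclusions on the primary endpoint. A reader who relies on the sentence will take the three contrasts as jointly controlled at 5%. The planning figure is affected too, because d_z 0.68 belongs to a single unadjusted paired t test.

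**Working it through.** **Inputs.** From Section 9.2: n = 20 (25 with 20% attrition), two-sided 5%, 80% power, d_z 0.68 and 0.89, an omnibus test on four means, three contrasts sharing Sham. From Section 9.6: random-intercept model, hence equal correlation between a participant's measurements. Assumed: complete data, normal errors, no carryover, and no period effect unless stated.

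**1. The plan's own figures.** Paired t test, df = 19, noncentrality d_z × √n.
- 0.68 × √20 = 3.04, giving power 82.2%. The detectable d_z at exactly 80% power is 0.66; 0.68 is the value for n = 19. The stated figure is slightly conservative.
- 0.89 × √20 = 3.98, giving power 96.5%, which agrees with the stated figure.
- 20 / (1 − 0.20) = 25, which agrees.

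The sample-size arithmetic is therefore sound for one test at 0.05.

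**2. Analytic check with two true nulls and the gate open.** Two contrasts sharing Sham have correlation σ²/(2σ²) = 0.5. For two standard normals with that correlation, P(|Z₁| > 1.96 or |Z₂| > 1.96) = 9.07%. Under independence it would be 1 − 0.95² = 9.75%.

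**3. Simulation of the procedure as written.** 200,000 trials per row, except that the d_z 0.3 row used 100,000. Omnibus F(3,57) at 5%, then the three contrasts at two-sided 0.05 on the pooled within-participant error. Family-wise error counts any rejection of a true null contrast.

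| True state | Gate opens | Family-wise error |
|---|---|---|
| No waveform works | 5% | about 4% |
| One works, d_z 0.3 | – | 5.9% |
| One works, d_z 0.68 | 87% | 8.9% |
| One works, d_z 0.89 | 99% | 9.0% |
| One works, larger effect | 100% | 9.1% |
| Two work, d_z 0.89 | 99.8% | 5.0% |

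If all three work there is no null contrast to reject falsely.

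**4. An order effect can open the gate.** Section 6.2.3 places 50 Hz last for everyone and concedes a potential order effect. If no waveform works but the 50 Hz mean is shifted by d_z 0.5 purely through order, the chance of a false rejection on Burst or 1 kHz is about 8%.

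**5. Two procedures that do control the error.**
- Fixed sequence in the listed order, each test at 0.05, stopping at the first non-significant result: simulated error 3.7% to 5.1% across the scenarios run. With all three effects at d_z 0.68, the power to reach and reject the first, second and third contrast is about 85%, 76% and 69% (pooled error).
- Holm on the three contrasts: simulated error 4.1% to 4.7%. The first step is at 0.05/3 = 0.0167. On the paired-t basis the detectable d_z is then 0.78, and power is 66.1% at d_z 0.68 (from 82.2%) and 89.9% at d_z 0.89 (from 96.5%).

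**The case against.** The best defence is that the contrasts are listed in an order and called hierarchical, so a fixed sequence may have been meant. On that reading the sentence would be correct and error would be at most about 5%. But the section neither makes the order binding nor says that testing stops. A sequence that is not written down does not control error, since the order could be settled after results are seen. What stands is that the smallest cure may simply be to write down what was intended.

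Four limits also stand:
- The inflation needs exactly one effective waveform. The protocol hypothesises that effective forms, in the plural, lower TS; with two effective, error is about 5%. The plan cannot rely on that in advance.
- The omnibus test itself holds its 5% level. Only the follow-up contrasts are affected.
- A reader might infer that any given inert waveform has nearly double the nominal chance of being declared effective. It does not: each null contrast is rejected about 5% of the time. The 9% is for at least one of two, in either direction; false claims of benefit make up about 4.5%, against a directional nominal rate of 2.5%.
- A reader might infer 12.5% because Section 9.6 does not repeat the gate. That is the error under no true effects with the gate ignored. Section 9.2 states the gate and Section 9.6 does not withdraw it.

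**Conclusion.** The sentence claims a property that the written procedure lacks. With 20 complete participants, family-wise error over the Sham contrasts is about 4% if no waveform works, about 5% if two work, and about 9% if exactly one works at either of the plan's own effect sizes. An order effect on 50 Hz alone, at a shift of d_z 0.5, gives about 8%.

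These figures rest on complete data, equal correlation, normal errors and no carryover. Missing treatment periods, which the per-protocol definition in Section 9.3 allows, would change them somewhat but not the logic.

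It would go too far to say that the error is 9% in general, or that between-waveform conclusions are compromised: the three named tests are all against Sham. The study also calls itself an exploratory pilot, so this should be fixed but does not undermine the trial.

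**What to change.** Replace the sentence in Section 9.2 with one of the following, and cite the choice in Section 9.6.

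- **(a) Fixed order.** Name the order of the three Sham contrasts, test each at two-sided 0.05, and stop at the first non-significant result. The d_z 0.68 planning figure then holds for the first test only; say that later tests have less power. If 50 Hz comes last, as in the present list, an order effect on its mean cannot open the way to the other two contrasts.
- **(b) Holm across the three contrasts.** Restate the planning figure: detectable d_z about 0.78 at the first step, and first-step power at d_z 0.68 of about 66% rather than 82%. That is a material loss on paper, though the first-step figure is the least favourable one. With pooled error, Holm's power per contrast at d_z 0.68 is about 72% if one waveform works and 79% if all three do.

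Under either option, say whether the omnibus test remains a condition for the contrasts. Keeping it does not raise the error, but it can cost power: with one effect at d_z 0.68 the gate opens 87% of the time.

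The cost is a few sentences in Sections 9.2 and 9.6, settled before unblinding, with no extra patients.
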